Participant number	A unique number assigned to each participant upon signing the informed consent. This number is the definitive, unique identifier for the participant and should be used to identify the participant throughout the study for all data collected, sample labels, etc.
Period	The subdivisions of the trial design (e.g. Screening, Treatment, Follow-up) which are described in the Protocol. Periods define the study phases and will be used in clinical trial database setup and eventually in analysis
Personal data	Participant information collected by the Investigator that is coded and transferred to Novartis for the purpose of the clinical trial. This data includes participant identifier information, study information and biological samples.
Premature participant withdrawal	Point/time when the participant exits from the study prior to the planned completion of all study drug administration and/or assessments; at this time all study drug administration is discontinued and no further assessments are planned
Screen Failure	A participant who did not meet one or more criteria that were required for participation in the study
Source Data/Document	Source data refers to the initial record, document, or primary location from where data comes. The data source can be a database, a dataset, a spreadsheet or even hard-coded data, such as paper or eSource
Start of the clinical trial	The start of the clinical trial is defined as the signature of the informed consent by the first participant
Study treatment	Any drug or combination of drugs or intervention administered to the study participants as part of the required study procedures; includes investigational drug(s), control(s) or background therapy
Study treatment discontinuation	When the participant permanently stops taking any of the study drug(s) prior to the defined study treatment completion date (if any) for any reason; may or may not also be the point/time of study discontinuation
Variable (or endpoint)	The variable (or endpoint) to be obtained for each participant that is required to address the clinical question. The specification of the variable might include whether the participant experiences an intercurrent event

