The first dose of DFV890 will be administered in the clinic and study treatment will be dispensed to the participant for continued treatment at home. Participants may be domiciled during the treatment period for convenience of the participants and/or logistical aspects, at the discretion of the participant and investigator.

Cold Challenge: Participants will be admitted to the clinic in the morning of Day 3, the day prior to cold challenge, and will be domiciled for a total of three days or longer if mandated by the investigator or by local regulations. On Day 3, participants will undergo safety assessments and then stay in a room with ambient temperature, preferably above 23°C, to ensure stable conditions prior to the cold challenge. On the morning of Day 4, pre-challenge assessments will be performed and breakfast will be served. Directly after breakfast, a pre-dose PK sample will be collected and the last dose of study treatment will be administered. One hour after study treatment administration, another PK sample will be collected, and the cold challenge will be initiated. The cold challenge lasts for 45 minutes. After the end of the cold challenge, participants will be monitored until the next morning (Day 5). The participants will be discharged after the last assessment on Day 5 or later, at the discretion of the investigator.

Follow up period

Participants will be followed-up for an end of study evaluation at the Study completion visit, approximately 10 days after last dose. The Study completion visit may be performed at an alternative Sponsor-approved site (e.g. satellite site that may be more convenient to the participant) if agreed by the principal investigator (PI) who will maintain the investigator responsibilities, and only as permitted by local regulations.

Unscheduled visits

Participants will be instructed to contact the investigator if they develop rash or pruritus between visits from Day 1 to the Study completion visit. An unscheduled visit should be considered based on clinical findings and severity of rash or pruritus and related assessments performed. Unscheduled visits may be performed at an alternative Sponsor-approved site (e.g. satellite site that may be more convenient to the participant) if agreed by the PI who will maintain the investigator responsibilities, and only as permitted by local regulations.

4 Rationale

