6.7.2 Instruction for prescribing and taking study treatment

Participants should take DFV890 b.i.d. at approximately the same time each day (+/- 1 hour if possible) in the morning and evening shortly after completion of a meal and with a glass of water. The morning meal should consist of at least a continental breakfast.

Participants should be instructed to swallow whole tablets and not to chew them.

If vomiting occurs during the course of treatment, participants should not take the study treatment again before the next scheduled dose.

Participants should be instructed not to make up missed doses. A missed dose is defined as a case when the full dose is not taken within 4 hours after the approximate time of the usually daily dosing. That dose should be omitted, and the participant should continue treatment with the next scheduled dose.

The first dose will be administered in the clinic, subsequent doses on Day 1 and 2 will be self-administered by the participant. Participants will be provided with individual diary cards to record each intake of study treatment and to confirm that study treatment was taken shortly after completion of a meal. The diary will be checked by site staff on Day 3.

On Day 3, the participant will administer the morning and evening dose of DFV890 after admission to the clinic, when instructed by the study staff. The last dose will be administered on the morning of Day 4. Participants will be provided a breakfast which should be consumed within 30 minutes. The study treatment should be administered within 5 minutes after completion of the meal.

Table 6-4 Dose and treatment schedule

Investigational Drug (Name and Strength)	Dose	Frequency and/or Regimen
DFV890 25 mg	100 mg (4 x 25 mg)	Twice daily (Day 1-3) Once daily (Day 4)

7 Informed consent procedures

Eligible participants may only be included in the study after providing (witnessed, where required by law or regulation), IRB/IEC-approved informed consent.

Informed consent must be obtained before conducting any study-specific procedures (e.g. all of the procedures described in the protocol). The process of obtaining informed consent must be documented in the participant source documents.

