9.1 Discontinuation and completion

9.1.1 Study treatment discontinuation and study discontinuation

Discontinuation of cold challenge

The cold challenge will be stopped, if any of the following criteria are met:

- The participant requests to discontinue the cold challenge
- The participant's body temperature is 35.0 °C or below (mild hypothermia*) on two consecutive temperature readings
- The criteria for an overall study stopping rule are met [Section 9.1.4](#)

Following stopping of the cold challenge the participant should immediately proceed to rewarming with monitoring, clinical assessments and complete other trial related procedures.

* Mild (hypothermia I) – 35.0-32.0 °C, clear consciousness with shivering, as defined by International Commission for Mountain Emergency Medicine ([Durrer et al 2003](#)).

Discontinuation of study treatment

Discontinuation of study treatment for a participant occurs when study treatment is permanently stopped for any reason prior to the protocol planned completion of study treatment administration. Discontinuation of study treatment can be initiated by either the participant or the investigator.

The investigator must discontinue study treatment for a given participant if, he/she believes that continuation would negatively impact the participant's well-being.

Discontinuation from study treatment is required under the following circumstances:

- Participant decision
- Pregnancy
- Use of prohibited treatment as per recommendations in the prohibited treatment section (see [Section 6.2.2](#))
- Any situation in which continued study participation might result in a safety risk to the participant
- Emergence of at least one of the following AEs:
 - A life-threatening adverse event (corresponding to a CTCAE Grade 4 or higher) unless clearly unrelated to DFV890 and/or the cold challenge
 - An adverse event of severe intensity (corresponding to a CTCAE Grade 3 or higher) unless clearly unrelated to DFV890 and/or the cold challenge
 - Skin rash, other than related to FCAS, greater than mild (covering >10% of the body surface area, corresponding to CTCAE grade 2 or higher), unless clearly unrelated to DFV890
- If an abnormal renal event is confirmed, and other causes are excluded, the study drug will be discontinued in the case of:

- Serum creatinine increase of 50% (i.e. acute kidney injury)
- New onset dipstick proteinuria $\geq 3+$
- Protein-creatinine ratio (PCR, gCr) ≥ 1 g/g

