- New evidence of clinically significant crystals on microscopy

Please refer to [Section 10.2.2](#) (Renal safety monitoring) and [Section 16.2, Table 16-4](#) and [Table 16-5](#) for further instructions and monitoring.

- Any laboratory abnormalities that in the judgment of the investigator, taking into consideration the participant's overall status, prevents the participant from continuing participation in the study
- If a liver event occurs, follow guidelines outlined in [Section 16.1](#) regarding discontinuation of study treatment

If discontinuation of study treatment occurs, the investigator should make a reasonable effort to understand the primary reason for the participant's premature discontinuation of study treatment and record this information.

Participants who discontinue study treatment or who decide they do not wish to participate in the study further should NOT be considered withdrawn from the study UNLESS they withdraw their consent (see [Section 9.1.2](#) 'Withdrawal of Informed Consent' section). **Where possible, they should return for the assessments indicated** in the Assessment Schedule ([Table 8-1](#)). If they fail to return for these assessments for unknown reasons, every effort (e.g. telephone, e-mail, letter) should be made to contact the participant/pre-designated contact as specified in the lost to follow-up section (see [Section 9.1.3](#)). This contact should preferably be done according to the study visit schedule.

If the participant cannot or is unwilling to attend any visit(s), the site staff should maintain regular telephone contact with the participant, or with a person pre-designated by the participant. This telephone contact should preferably be done according to the study visit schedule.

After study treatment discontinuation, at a minimum, in abbreviated visits, the following data should be collected at clinic visits or via telephone/email contact:

- New / concomitant treatments
- AEs / SAEs

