9.1.4 Study stopping rules

Overall study stopping rules

The study will be stopped, and no further dosing and/or new recruitment will occur, pending full safety review by the sponsor and the investigator, if any of the following criteria are met:

- Any death or life-threatening event (corresponding to CTCAE grade 4 or higher) unless clearly unrelated to DFV890 and/or the cold challenge
- Any SAE (other than death or life-threatening event, corresponding to CTCAE grade 3 or higher) unless clearly unrelated to DFV890 and/or the cold challenge
- Two (2) or more participants are discontinued due to a renal event as defined in [Section 16.2](#)
- Two (2) participants experience an AE of similar type which is assessed as severe in intensity (corresponding to CTCAE grade 3 or higher) unless clearly unrelated to DFV890
- Number and/or severity of AEs, abnormal safety monitoring tests, or abnormal laboratory findings justify putting the study on hold

The safety review will be conducted jointly between medically qualified representatives of the sponsor and the investigators. The study may resume following the safety review, if the investigator and sponsor agree it is safe to proceed and necessary approvals have been obtained from authorities.

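### The renal stopping criterion in Section 9.1.4 counts participants who are discontinued, so on its natural reading a qualifying renal event first found after the last dose does not add to the count of two

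*Protocol*

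**What the plan says.** Protocol Section 9.1.4 lists five criteria, any of which halts dosing and/or recruitment pending a safety review. The third is the only one specific to the kidney: "Two (2) or more participants are discontinued due to a renal event as defined in" Section 16.2. It does not say whether the discontinuation is from study treatment or from the study.

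Section 9.1.1 defines discontinuation of study treatment as treatment being "permanently stopped for any reason prior to the protocol planned completion of study treatment administration". The glossary agrees: the participant "permanently stops taking any of the study drug(s) prior to the defined study treatment completion date". The renal criteria in 9.1.1 concern the drug: "If an abnormal renal event is confirmed, and other causes are excluded, the study drug will be discontinued in the case of" a 50% rise in serum creatinine, new dipstick proteinuria of 3+ or more, a protein-creatinine ratio of at least 1 g/g, or new clinically significant crystals.

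On timing, Section 6.7.2 states: "The last dose will be administered on the morning of Day 4". Section 6.5 allows one extra day in exceptional circumstances, which moves the last dose to Day 5. Section 10.2.2 has renal alert values assessed over the study period once a participant has been exposed, with findings confirmed within 24 to 48 hours. Table 8-1 schedules urinalysis and clinical chemistry at Study completion, on Day 14 with a window of -0 to +7 days.

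**The concern.** The renal criterion is triggered by an action (stopping) rather than by the event itself. After a course of about three days, that action is no longer available for most of the time in which renal findings are sought. Two participants could each have a confirmed 50% creatinine rise, which 9.1.1 describes as acute kidney injury, and the study's one renal-specific criterion would not register either of them if both rises were first seen at Study completion.

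This matters because Section 4.6.4 names renal abnormality as a potential risk, while saying that an effect on the human kidney is unclear. Section 4.6.11 relies on renal monitoring and stopping rules to keep risk low. The sponsor chose a fixed count of two for this risk. Whether a case counts should not depend on whether the sample was drawn before or after the last tablet. Those affected are participants not yet dosed, whose treatment the rule is meant to pause.

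**Working it through.** The documents state no operating characteristic for this rule, so there is no figure to reproduce. The check consists of reading the definitions together, a timeline and a count.

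**Which discontinuation is meant.** Three things point to study treatment. The renal criteria in 9.1.1 stop the drug. Section 9.1.1 also says that participants who stop treatment are not withdrawn from the study unless they withdraw consent, and should return for assessments where possible. Table 16-5 keeps a participant with a renal event under observation until it resolves or stabilizes. A renal event therefore normally ends dosing but not participation.

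**Timeline.**
- Last dose: Day 4 morning (6.7.2), or Day 5 (6.5).
- Study completion: Day 14 to Day 14 + 7 = Day 21 (Table 8-1).
- Gap after a Day 4 last dose: 14 - 4 = 10 days to 21 - 4 = 17 days.
- Gap after a Day 5 last dose, if the visit day is not shifted: 14 - 5 = 9 days to 21 - 5 = 16 days.
- Confirmation 24 to 48 hours after a finding at that visit: Day 15-16 at the earliest visit, Day 22-23 at the latest.

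Both detection and confirmation fall after dosing, so there is no treatment left to discontinue.

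**Findings during dosing.** Day 3 assessments precede the morning dose (Table 8-1, footnote 3), about 48 hours after the first dose. Taking the full 24 to 48 hours to confirm leads to 48 + 24 = 72 to 48 + 48 = 96 hours, while the last dose is at about 72 hours. A stop need not wait for confirmation, however. Section 9.1.1 also requires it for "Any situation in which continued study participation might result in a safety risk to the participant" and for "Any laboratory abnormalities that in the judgment of the investigator" prevents continued participation. Section 3 also places a check before the last dose: "On the morning of Day 4, pre-challenge assessments will be performed and breakfast will be served". A Day 3 or pre-dose Day 4 finding can therefore count if the remaining dosing is stopped.

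**Count under the renal criterion for two participants with qualifying events (treatment reading).**

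| Scenario | As written | Reworded |
|---|---|---|
| Both stopped before the last dose | 2 | 2 |
| One stopped, one first found after the last dose | 1 (not met) | 2 |
| Both first found after the last dose | 0 (not met) | 2 |

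The Day 4 and Day 5 columns of Table 8-1 could not be read reliably in the text available. Nothing here rests on them.

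**The case against.** The strongest reply is that the same list already covers these events. Criteria 1, 2 and 4 are not tied to dosing. A late renal event that is life-threatening, or a serious one under criterion 2, can stop the study on its own, as can two severe events of similar type. Table 16-4 says to consider hospitalization for a 50% creatinine rise, and Section 10.1.2 makes inpatient hospitalization a seriousness criterion. One such case could therefore be enough, subject to the grade 3 wording of criterion 2. The last criterion names abnormal laboratory findings, and once it is judged to be met the stop is as mandatory as under the others. All of this stands. It narrows the gap to late events that are neither serious nor severe and show only in the laboratory. For those, the last criterion depends on judgment and has no count.

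A second reply is that discontinued may mean discontinued from the study. The title of 9.1.1 covers both kinds, and the glossary entry on premature withdrawal includes leaving before assessments are complete. This also stands in part. A reader might infer that late events can never count, but the documents do not establish that, because the term is undefined. An ambiguous trigger in a mandatory rule still needs settling.

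Two further inferences should be resisted. One is that the study could not be stopped for late renal events; the other criteria show that it could. The other is that the renal criterion cannot work at all in so short a course; the safety-risk and investigator-judgment grounds in 9.1.1 allow dosing to be stopped before confirmation.

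Finally, monitoring that reaches further than a stopping rule is not a fault in itself, since late tests also serve individual follow-up. That is fair. The fault is that the trigger is undefined and, as most naturally read, omits qualifying events because of when they were found.

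**Conclusion.** The point holds as a gap in one criterion. On the natural reading, a qualifying renal event first found after the last dose does not add to the count of two, and no text extends the count to such events. What is missing is a fixed trigger for late, laboratory-only renal events. The ability to stop the study for them is not missing.

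The size is the difference in the count: 1 instead of 2 with one late case, 0 instead of 2 with two. This assumes that discontinuation means study treatment and that the late events meet the 9.1.1 thresholds with other causes excluded. The documents give no renal event rate, no share of events expected after dosing and no enrolment timing. No probability, and no number of participants exposed to risk, can be derived or is claimed. The change is worth making because it is cheap and concerns a risk that the protocol itself singles out.

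**What to change.** Reword the third criterion of Section 9.1.4 so that it is met when two or more participants fall under either limb:

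- (a) they discontinue study treatment because of a renal event under Section 16.2; or
- (b) they have a renal event that meets the renal criteria of Section 9.1.1, with other causes excluded, that is first detected at any time from first dose up to and including the Study completion visit and is subsequently confirmed (including by a repeat assessment after that visit), whether or not dosing was ongoing.

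Naming study treatment in limb (a) removes the ambiguity. In limb (b) the window must attach to first detection. If it attached to confirmation, an event found at Study completion and confirmed one or two days later could again fall outside.

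The cost is one sentence in an amendment. Thresholds do not change. No tests or visits are added, because the Study completion laboratory tests are already scheduled, Section 10.2.2 already requires confirmation, and Section 9.2 already provides for repeat assessments linked to that visit. The downside is that the study may pause somewhat more readily. Under Section 9.1.4 it may resume once the safety review is done and the necessary approvals are in place.

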9.1.5 Early study termination by the sponsor

The study can be terminated by Novartis at any time.

Reasons for early termination

- Unexpected, significant, or unacceptable safety risk to participants enrolled in the study
- Discontinuation of study drug development

In taking the decision to terminate, Novartis will always consider participant welfare and safety. Should early termination be necessary, participants must be seen as soon as possible (instructions for contacting the participant, when the participant should stop taking drug, when the participant should come in for a final visit, will be provided at that time) and treated as a prematurely withdrawn participant. The investigator may be informed of additional procedures to be followed in order to ensure that adequate consideration is given to the protection of the participant's interests. The investigator or sponsor depending on local regulation will be responsible for informing IRBs/IECs of the early termination of the trial.

9.2 Study completion and post-study treatment

Study completion is defined as when the last participant finishes their Study completion visit and any repeat assessments associated with this visit have been documented and followed-up appropriately by the Investigator or, in the event of an early study termination decision, the date of that decision. Each participant will be required to complete the study in its entirety and thereafter no further study treatment will be made available to them.

All treated participants should have a safety follow-up call conducted 30 days after last administration of study treatment. The information collected is kept as source documentation. All SAEs reported during this time period must be reported as described in [Section 10.1.3](#). Documentation of attempts to contact the participant should be recorded in the source documentation.

Continuing care should be provided by the investigator and/or referring physician. No further study treatment will be provided.

10 Safety monitoring and reporting

10.1 Definition of adverse events and reporting requirements

10.1.1 Adverse events

An adverse event (AE) is any untoward medical occurrence (e.g. any unfavorable and unintended sign [including abnormal laboratory findings], symptom or disease) in a clinical investigation participant after providing written informed consent for participation in the study. Therefore, an AE may or may not be temporally or causally associated with the use of a medicinal (investigational) product.

The investigator has the responsibility for managing the safety of individual participant and identifying AEs.

Novartis qualified medical personnel will be readily available to advise on trial related medical questions or problems.

The occurrence of AEs must be sought by non-directive questioning of the participant at each visit during the study. AEs also may be detected when they are volunteered by the participant during or between visits or through physical examination findings, laboratory test findings, or other assessments.

AEs must be recorded under the signs, symptoms, or diagnosis associated with them, accompanied by the following information (as far as possible) (if the event is serious refer to [Section 10.1.2](#)):

1. The severity grade
 - mild: usually transient in nature and generally not interfering with normal activities
 - moderate: sufficiently discomforting to interfere with normal activities
 - severe: prevents normal activities
2. Its relationship to the study treatment. If the event is due to lack of efficacy or progression of underlying illness (i.e. progression of the study indication) the assessment of causality

will usually be 'Not suspected.' The rationale for this guidance is that the symptoms of a lack of efficacy or progression of underlying illness are not caused by the trial drug, they happen in spite of its administration and/or both lack of efficacy and progression of underlying disease can only be evaluated meaningfully by an analysis of cohorts, not on a single participant

3. Its duration (start and end dates) or if the event is ongoing, an outcome of not recovered/not resolved must be reported
4. Whether it constitutes a SAE (see [Section 10.1.2](#) for definition of SAE) and which seriousness criteria have been met
5. Action taken regarding with study treatment. All AEs must be treated appropriately. Treatment may include one or more of the following:
 - Dose not changed
 - Dose reduced/increased
 - Drug interrupted/withdrawn
6. Its outcome (i.e. recovery status or whether it was fatal)

Conditions that were already present at the time of informed consent should be recorded in medical history of the participant.

AEs (including lab abnormalities that constitute AEs) should be described using a diagnosis whenever possible, rather than individual underlying signs and symptoms.

AE monitoring should be continued until the end of the study visit.

Once an AE is detected, it must be followed until its resolution or until it is judged to be permanent (e.g. continuing at the end of the study), and assessment must be made at each visit (or more frequently, if necessary) of any changes in severity, the suspected relationship to the interventions required to treat it, and the outcome.

Information about adverse drug reactions for the investigational drug can be found in the IB.

Abnormal laboratory values or test results constitute AEs only if they fulfill at least one of the following criteria:

- they induce clinical signs or symptoms
- they are considered clinically significant
- they require therapy

Clinically significant abnormal laboratory values or test results must be identified through a review of values outside of normal ranges, significant changes from baseline or the previous visit, or values which are considered to be non-typical in participant with the underlying disease.

